General. Baseline clinical and demographic characteristics will be collected and contrasts performed between treatment groups. Continuous and ordinal characteristics will be compared using a Wilcoxon Rank-Sum test statistic. Categorical characteristics will be compared using a Pearson Chi-Square test statistic. Baseline characteristics found to be significantly associated with primary outcome measures will be included as covariates in the analyses. All analyses will be performed on the intent-to-treat sample consisting of all randomized subjects. All analysis will be conducted using SAS v9.3 (SAS Institute, Cary, NC, USA).

Randomization. We will stratify by (1) AUD severity (TLFB) and (2) PTSD severity (CAP-5). Stratified random block randomization will be used to balance the randomization assignment with respect to these strata. The purpose of stratification is to distribute these potential prognostic factors equally across treatment groups.

Power and Sample Size. This study is powered to estimate the efficacy of NAC on the reduction in PTSD symptoms, alcohol use, and craving at the end of the treatment phase (final 3 weeks of treatment). This study builds on a recently completed pilot trial of NAC that assessed efficacy in reduction of PTSD symptomology and craving in a cohort of Veterans with PTSD and substance use disorders. In this promising pilot trial, we observed a clinically significant decrease in CAPS total scores following 8 weeks of treatment with NAC ($\Delta=26.8$) while the placebo response was attenuated ($\Delta=17.1$). Assuming a similar difference in treatment effects in a larger population, we will have 80% power with a type 1 error rate of 5% to detect this difference with 75 participants randomized to each of the two treatment arms (total

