N=150). In the same pilot trial, 77% of subjects completed the 8 week trial; we anticipate similar retention in the proposed study. Thus, a randomized sample size of 100 participants per treatment arm (total N=200) would maintain power to detect the clinically significant difference stated above in the presence of ~25% attrition during the study. Similarly, in the same pilot study, reductions in craving were significantly greater in the NAC vs. placebo treated group ($\Delta=3.0$ vs. $\Delta=1.3$). The randomized sample size of 100 per treatment arm provides >95% power with a type 1 error rate of 5% to detect this effect in the presence of 25% attrition during the study period. It is hypothesized that NAC reduces the risk of drinking as compared to placebo. With this stated sample size, a 25% decreased risk in the consumption of standard drinks can be detected with at least 80% power between the NAC and placebo treated arms (Risk Ratio=0.75).

Power calculations for the neuroimaging component are based on previous studies of individuals with PTSD or substance use disorders. Based on our previous work and the extant literature, we conservatively estimate ~70% of participants (140/200) will be eligible and volunteer for the neuroimaging component. A recent study of 29 individuals (PTSD=14, controls=15) observed significant differences in PFC-AMY resting state connectivity⁵⁰. The effect size for this difference was 0.8 (Cohen's d). Thus, power (1- β) reaches .80 with a total sample size of N=26 (two-tailed, alpha=.05). Another study of 45 cocaine-dependent individuals found that individuals who relapsed (n=24) had significantly lower PFC-AMY connectivity at baseline as compared to individuals who did not relapse (n=21)⁴⁹. The effect size for this reduction was 1.0. Thus, power (1- β) reaches .80 with N=34 subjects (two-tailed, alpha=.05). For exploratory hypothesis 4, the only published study of NAC effects on brain glutamate found that one dose of NAC vs. placebo administered 1 hour prior to scanning, led to a significant modification in ACC glutamate with an effect size of $d = 2.6$ in individuals with cocaine dependence. Although the present study will be examining the effects of chronic NAC treatment in individuals with AUD and PTSD, an effect of similar magnitude would provide power > 0.99. The present study is therefore well-powered to test the proposed hypotheses.

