For hypotheses 3A and 3B, the following preprocessing and analytical parameters will be used. Preprocessing: Post-acquisition preprocessing and statistical analysis of imaging data will be performed using FEAT (FMRI Expert Analysis Tool) Version 5.98, part of FSL (FMRIB's Software Library). Data will be preprocessed using scripting tools from FEAT. Non-brain signal will be removed using FSL's BET brain extraction. Scans will be corrected for motion using FSL's linear registration and scans will be spatially smoothed using a Gaussian kernel of 8 mm FWHM. Participants with head motion ≥ 0.2 mm will be excluded from the analyses¹²⁷. Motion artifacts will be identified and scrubbed from each subject's data. Scans will be spatially co-registered with a standardized anatomical template (Montreal Neurological Institute) using a 12 parameter affine transformation. Analysis: Functional connectivity will be measured using a psychophysiologic interaction seed-based approach¹²⁹⁻¹³⁰. PPI analysis is used to assess the functional coupling between different brain regions. The PPI is defined as the change in connectivity of one area (i.e., the seed region) to another in relation to the experimental context (e.g., alcohol vs. neutral cues). PPI analyses for resting state, trauma and alcohol cues will be performed separately. Customized sq. wave forms representing the trauma run (1=trauma block and -1=neutral block) and the alcohol cue run (1=alcohol block and -1=neutral block) the duration of each block will be convolved with a double-gamma hemodynamic response function. A mask of the seed region will be made using a 12-mm diameter sphere located in the center of the AMY using the MNI coordinates (x, y, z = ± 22 , 0, -22). The transformation parameters described above will also be applied to the mask. For each subject, the mean corrected and high pass filtered time series of the BOLD signal in the AMY will be extracted and used in a single subject whole brain PPI analysis. The PPI model will include the task vector, time series of the BOLD signal in the AMY, a term representing the positive task x seed interaction, and a term representing the negative task x seed interaction. The first level analysis will generate contrast images of the parameter estimates for each of the four regressors. Voxels will be thresholded at $Z > 2.3$ using a corrected cluster threshold of $p = 0.05$. The contrast images of the parameter estimates of the positive and negative task x seed interactions will be combined for group-level t-tests to identify regions that exhibited altered connectivity with the AMY during the trauma and alcohol cues as compared to neutral cues. All group-level results will be thresholded at $Z > 2.3$ using a corrected cluster threshold of $p = 0.05$. Separate linear regression tests will be used to test for associations between PFC-AMY connectivity at baseline and improvement in AUD and PTSD symptoms during treatment. Changes in total standard drinks will be regressed against the parameter estimate obtained from the center voxel from each cluster that exhibited a significant task x seed interaction with the AMY at rest and in response to the alcohol cues (Hypothesis 3A). Changes in CAPS-5 total scores will be regressed against the parameter estimate obtained from the center voxel from each cluster that exhibited a significant task x seed interaction with the AMY at rest and in response to the trauma cue (Hypothesis 3B). Further exploratory analyses will examine change in PFC-AMY connectivity from pre- to post-treatment and associations with alcohol and PTSD outcomes, both within and between medication groups.

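### Hypotheses 3A and 3B regress a single change score with no stated end point, so imaged participants who leave early may fall out of the prognostic test although on-treatment outcomes exist for some of them

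*Combined protocol and SAP*

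**What the plan says.** Under Statistical Analyses, Hypotheses 3A and 3B, separate linear regressions test "associations between PFC-AMY connectivity at baseline and improvement in AUD and PTSD symptoms during treatment". For 3B, "Changes in CAPS-5 total scores will be regressed against the parameter estimate obtained from the center voxel from each cluster" showing a significant interaction with the amygdala seed. For 3A the outcome is the change in total standard drinks. Neither the end point of the change nor the handling of a missing change is stated.

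Elsewhere in the protocol/SAP:

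- Power and Sample Size expects about 140 of 200 participants to be imaged. It sets the randomized number so that power holds "in the presence of ~25% attrition during the study". That allowance belongs to the main comparison; none is given for imaging. The same section describes the end of the treatment phase as the last three weeks, but the imaging regressions do not refer to this.
- Statistical Analyses, General states: "All analyses will be performed on the intent-to-treat sample consisting of all randomized subjects".
- Mixed models are specified for Hypotheses 1 and 2 and for glutamate change in Hypothesis 4, but not for 3A and 3B.
- TLFB is collected weekly during treatment (Primary Outcome Measures). Table 1 and its footnote schedule CAPS-5 at baseline, at Week 6, before imaging sessions and at Week 12.

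**The concern.** A linear regression with one outcome per person omits anyone whose outcome is missing. If the change is taken to Week 12, a participant who was scanned at baseline and left in Week 8 contributes nothing, even with a Week 6 CAPS-5 and several weeks of TLFB on file. Aim 3 asks whether baseline connectivity predicts outcome. Scans already acquired would go unused, and the slope could be biased if the chance of leaving is related to how the participant was doing. Because the end point is not named, it could also be chosen after the data are seen.

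**Working it through.** **1. The plan's own imaging figures.** For the relapse comparison, "The effect size for this reduction was 1.0", and power "reaches .80 with N=34 subjects (two-tailed, alpha=.05"). A two-sample t-test with d = 1.0, two-sided alpha 0.05 and power 0.80 needs 16.7, so 17 per group or 34 in total (power 0.807). This reproduces. For the resting-state comparison, "The effect size for this difference was 0.8 (Cohen's d"), and power "reaches .80 with a total sample size of N=26 (two-tailed, alpha=.05"). This does not reproduce as a total: 25.5, so 26, is the number per group, or 52 in total. That is a separate matter, since both 140 and 105 exceed 52.

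**2. The attrition step.** 75 / (1 − 0.25) = 100 per arm, which matches N = 200.

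**3. How many could be lost from 3A and 3B.** The plan gives no imaging-specific rate, so the whole-trial rate is carried over as an assumption.

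- At 25% loss: 140 × 0.75 = 105 with a Week 12 value, so 35 without.
- At the pilot's 77% completion: 140 × 0.77 ≈ 108, so about 32 without.
- If an earlier on-treatment value may serve as the end point, the number without any change score lies between 0 and 35. The documents do not give the timing of drop-out.

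Head-motion exclusions would reduce the sample further, at a rate that the plan does not state.

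**4. Precision.** Standard-error ratio = √(140/105) = 1.155, so up to about 15% larger.

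**5. Power.** Convert d to a correlation by r = d/√(d² + 4): d = 0.8 gives 0.371, and d = 1.0 gives 0.447. By Fisher's z, power = Φ(atanh(r)·√(n − 3) − 1.96).

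| r | n = 140 | n = 105 |
|---|---|---|
| 0.447 (d = 1.0) | >0.99 | >0.99 |
| 0.371 (d = 0.8) | 0.995 | 0.976 |
| 0.25 (assumed) | 0.85 | 0.73 |

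The smallest correlation detectable with 80% power rises from 0.235 to 0.270.

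**6. Direction of bias.** Large-sample simulation with standard normal connectivity and outcome and 75% retained. The table gives the slope among those retained, divided by the true slope, across true correlations of 0.25, 0.371 and 0.447.

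| Assumed drop-out mechanism | Ratio |
|---|---|
| Random, or dependent on connectivity only | 1.00 |
| Moderately dependent on outcome (logit slope 0.5 to 1) | 0.96 to 0.88 |
| Worst quarter of outcomes all lost | 0.55 to 0.59 |
| Connectivity and outcome push retention the same way | 0.53 to 0.75 |
| Connectivity and outcome push retention in opposite ways | 1.13 to 1.33 |

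**7. What a longitudinal model recovers.** Simulation with 140 imaged. Assumptions: true correlation 0.25 with Week 12 change, Week 6 to Week 12 correlation 0.7, about 24% loss, roughly half of it before Week 6. Ranges cover repeat runs.

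| Loss mechanism | Completer power | Longitudinal power | Completer slope bias | Longitudinal slope bias |
|---|---|---|---|---|
| Unrelated to outcome | 74% | 77% | none | none |
| Log-odds 0.7 per SD of poor response | 72–73% | 76–77% | −3% to −4% | −1% to −2% |
| Log-odds 1.2 per SD of poor response | 69–71% | 73–75% | −9% to −10% | about −6% |

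Power with every outcome observed is 85%. If leaving depends directly on the outcome at each visit, the completer bias is larger (6% to 15%) and the longitudinal model removes less of it (5% to 11% remains).

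**The case against.** The case against is substantial, and much of it stands.

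- **A quarter of scans certainly lost.** A reader might infer this, but the documents do not support it. The 25% is a whole-trial figure derived from an 8-week pilot, and no rate is given for imaging volunteers. The regression text refers only to improvement during treatment. Weekly TLFB, a Week 6 CAPS-5 and possibly one before the second scan mean that many who leave could still have some change score. For 3A in particular, 35 is a loose upper bound.
- **A completers-only analysis by design.** The plan does not say this. It is what ordinary regression does by default if Week 12 is the end point.
- **A weakened association.** This is not established. The slope is unbiased if loss is random or depends only on connectivity, and some mechanisms inflate it.
- **A breach of the all-randomized statement.** This argument is weak. Imaging is optional, about 140 of 200 are expected, and head motion excludes more, so no version of Aim 3 could include everyone randomized. The longitudinal model would not do so either.
- **Little to gain.** At the plan's own effect sizes there is no power problem. At the smaller assumed effect, the longitudinal model adds only about 3 to 4 points of power and leaves part of the bias. Change-score regression is also a common choice for a prognostic marker.

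None of this answers the central point. The end point and the missing-outcome rule are absent, and the stated method discards repeated outcomes that the trial's other hypotheses would use.

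**Conclusion.** The concern holds in a limited form. Hypotheses 3A and 3B use one change score with an unstated end point and no missing-outcome rule. If the end point is Week 12 and whole-trial attrition applies to imaging, up to about 35 of 140 scanned participants drop out of the regression. The firm cost is precision: a standard error up to about 15% larger. Bias is possible, not demonstrated. It is about 3% to 10% attenuation under moderate assumed outcome-related loss, and it could be inflation under joint selection. The correlation of 0.25, the between-visit correlation, the drop-out timing and the drop-out strength are all assumptions from outside the documents. Power at d = 0.8 to 1.0 stays at about 0.98 or more, so the case rests on a defined estimand and on use of the data collected, not on a failure of power. This is a worthwhile, inexpensive improvement with a modest gain.

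**What to change.** Amend the analysis text for Hypotheses 3A and 3B as follows.

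1. Name end of treatment (Week 12) as the target time point for both.
2. For 3B, fit a mixed model to CAPS-5 at Week 6 and Week 12 in all imaged participants with any on-treatment value. Include baseline CAPS-5, treatment arm, visit, connectivity and connectivity × visit, and test the connectivity slope at Week 12. The arm term matters because drop-out may differ by arm.
3. For 3A, model the weekly TLFB drinks in the Hypothesis 1 longitudinal framework with baseline drinks, treatment arm and connectivity. State that a log-link count model reports a rate ratio and not a change in drinks.
4. Keep the change-score regression as a sensitivity analysis, with the number of participants it omits.

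The cost is SAP wording and a little more analysis work, with no new data or visits. Two drawbacks should be acknowledged. The result relies on missing-at-random, so it does not remove bias from loss that depends on unobserved outcomes, and the effect scale for 3A changes.

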Hypotheses. The hypotheses and statistical approaches for testing each hypothesis are listed below.

Hypothesis 1: NAC treatment will result in significantly greater reduction in AUD severity and craving, as compared to placebo. To test this hypothesis, a mixed effects modeling framework will be specified with the total number of standard drinks consumed and the OCDS total score as the primary outcomes. A Poisson distribution will be assumed with a logarithm link function to assess the effects of NAC treatment and the baseline number of total standard drinks (past 60 days) prior to treatment entry. Over-dispersion due to a wider than expected distribution in discrete count models (from heterogeneity) can have a significant impact on parameter inference, thus when detected, a negative binomial (NB) distribution will be specified. Further, data collected in substance abuse studies often contain a preponderance of zeros, and these zeros in the distribution can be considered sampling zeros in the Poisson process¹²⁵. If this excess is present in the distribution, two-part Hurdle models (Poisson and NB) will be explored¹²⁶⁻¹²⁷. The hurdle part of the model will allow us to estimate the probability of abstinence during the study period (as an odds ratio) while the Poisson/NB portion will allow for the assessment of the risk of an increase in using days beyond zero during the study period (as a risk ratio). Model fit of the Poisson (Hurdle Poisson) model will be compared to the Negative Binomial (Hurdle NB) model by practical examination of the deviance and Pearson chi-square values (Likelihood Ratio) with respect to their degrees of freedom. Baseline alcohol use and craving will be included in pertinent models as covariates. Additional alcohol use outcomes will be assessed: percentage of drinking days (DD) and the number of heavy drinking day (HDD). End of study abstinence will be assessed using logistic regression models. DD and HDD will be assessed using count models.

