Hypothesis 2: NAC treatment will result in significantly greater reduction in PTSD severity as compared to placebo. To test this hypothesis, generalized linear mixed effects regression models with a Gaussian distribution will be developed to assess group differences while adjusting for baseline CAPS-5 scores. Assumptions of residual normality and homoscedasticity will be checked using statistical test and graphical methods (Residual and Q-Q plots, and Shapiro-Wilk tests) and transformation will be done as necessary. Restricted maximum likelihood (REML) methods will be used to estimate the fixed effects and variance components.

Hypothesis 3A: Prefrontal cortex-amygdala connectivity at rest and in response to alcohol vs. neutral cues will predict reduction in alcohol use severity (total standard drinks).

Hypothesis 3B: Prefrontal cortex-amygdala connectivity at rest and in response to trauma vs. neutral cues will predict reduction in PTSD severity (CAPS-5).

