
Exploratory Hypothesis 4: NAC treatment will be associated with a significant change in ACC glutamate concentrations, as compared to placebo. Change in ACC glutamate concentrations will be associated with alcohol and PTSD outcomes.

Analysis of PRESS data will be conducted using LC Model 6.3¹³¹, an operator-independent curve-fitting software package that uses least-squares estimation for quantifying metabolite concentrations; the basis set for TE = 40ms is provided by the vendor and includes a number of metabolites including glutamate, creatine, glutamine, N-acetylaspartate, and phosphocholine. Only metabolites with fitting uncertainties (Cramer-Rao Lower Bound values) $< 20\%$ of SD in the LC Model output will be retained for analysis. LC Model includes standardized zero filling, Fourier transformation, and automated phase, baseline and eddy current correction. To address variability in within-voxel tissue composition we will extract and segment T₁-weighted images into partial volume maps of gray matter (GM), white matter (WM), and CSF using FSL tools, match the coordinates and size of the ¹H-MRS voxel with the segmented images and extract the tissue fractions within the voxel, correct the raw values obtained from the LC model (scaled

to water) for CSF and coil loading, and calculate each participant's GM to brain matter (GM/[GM+WM]) ratio for use as a covariate in the analyses. Change in glutamate levels will be analyzed as a mixed model (SAS PROC MIXED) with time as a within subject variable and medication group as between subject variables. Variables known to influence ACC glutamate levels (e.g., age, smoking status, tissue composition) will be considered as covariates. Further exploratory regression analyses will examine associations between glutamate difference scores and clinical outcomes (e.g., change in total standard drinks and CAPS-5 score) both within and between medication groups.

Summary: The proposed study will answer important questions regarding the potential of NAC as an effective pharmacotherapy for AUD and comorbid PTSD, and elucidate possible mechanisms underlying improved outcomes. The findings from this study have the potential to significantly improve the standard of patient care and accelerate research on the treatment of AUD and co-occurring PTSD

REFERENCES

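### Hypothesis 3B regresses raw CAPS-5 change on baseline connectivity without pre-specifying baseline CAPS-5 as a covariate, so a marker that only tracks entry severity could look prognostic

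*Combined protocol and SAP*

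**What the plan says.** All references are to Statistical Analyses in the combined protocol and SAP.

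- **Hypotheses 3A and 3B, analysis text.** The regression step opens: "Separate linear regression tests will be used to test for associations between PFC-AMY connectivity at baseline and improvement in AUD and PTSD symptoms". For 3B it continues: "Changes in CAPS-5 total scores will be regressed against the parameter estimate obtained from the center voxel" of each cluster with a significant interaction, at rest and under the trauma cue. No covariate is named.
- **Hypothesis 2.** The treatment comparison on PTSD severity uses a mixed model "to assess group differences while adjusting for baseline CAPS-5 scores".
- **Hypothesis 1.** "Baseline alcohol use and craving will be included in pertinent models as covariates". This covers alcohol use and craving. It does not mention CAPS-5.
- **General.** "Baseline characteristics found to be significantly associated with primary outcome measures will be included as covariates in the analyses". The rule names no variable and is conditional on a finding in the data.
- **Randomization.** PTSD severity is a stratification factor, and the plan describes its strata as possibly prognostic.

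**The concern.** A change score contains the baseline score. When baseline and follow-up are imperfectly correlated, people who start higher tend to fall further. Any predictor that is correlated with the starting score therefore picks up a correlation with change, even if it carries no information about who improves from a given starting point.

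In Hypothesis 2 randomisation protects against this, and baseline adjustment mainly buys precision. In Hypothesis 3B the predictor is an observed brain measure, so nothing balances entry severity across its values. The plan treats entry severity as possibly prognostic when it randomises, but does not fix it in the model that tests a prognostic marker for PTSD.

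At stake is the meaning of a positive 3B result. It might show that connectivity predicts improvement, or only that more severe patients have further to fall.

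**Working it through.** **Plan's own figure.** The plan gives no sample-size calculation for the 3B regression. The nearest is the relapse contrast in Power and Sample Size: d = 1.0, two-sided 5%, 80% power, N = 34. A two-sample t-test needs 16.7, so 17 per group and 34 in total. The figure reproduces, but it is a two-group comparison and does not depend on this point.

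**Inputs from the documents**
- Imaging sample: 140 of 200.
- Attrition of about 25%. If it applies equally to the imaging subset (an assumption), 140 × 0.75 = 105.

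**Inputs assumed, because the documents give none**
- r = correlation of baseline with follow-up CAPS-5: 0.5, range 0.3 to 0.7, with equal SDs.
- ρ = correlation of connectivity with baseline CAPS-5: 0, 0.2, 0.3.
- Null model: follow-up depends on connectivity only through baseline CAPS-5.

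**Step 1: spurious correlation.** Take change as baseline minus follow-up and set both SDs to 1. The covariance of connectivity with change is ρ − rρ = ρ(1 − r). The SD of change is √(2(1 − r)). Hence

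corr(connectivity, change) = ρ√((1 − r)/2).

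At r = 0.5 this is 0.2 × 0.5 = 0.10, or 0.3 × 0.5 = 0.15.

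**Step 2: rejection rate at nominal two-sided 5%, by Fisher z.** For correlation 0.15 and n = 105: atanh(0.15) × √102 = 0.1511 × 10.10 = 1.526, and Φ(1.526 − 1.96) = 0.33. For n = 140: 0.1511 × √137 = 1.769, and Φ(1.769 − 1.96) = 0.42.

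| r | ρ | n = 105 | n = 140 |
|---|---|---|---|
| 0.3 | 0.2 | 22% | 28% |
| 0.3 | 0.3 | 44% | 56% |
| 0.5 | 0.2 | 17% | 22% |
| 0.5 | 0.3 | 33% | 42% |
| 0.7 | 0.2 | 12% | 15% |
| 0.7 | 0.3 | 22% | 28% |

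Simulation with 10,000 trials per setting agrees: 33.5% and 42.8% at r = 0.5, ρ = 0.3. With baseline CAPS-5 in the model the simulated rate is about 5% in every setting. At ρ = 0 both models hold about 5%.

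**Step 3: precision when ρ = 0.** The variance of raw change is 2(1 − r). Its residual variance given baseline is 1 − r². The ratio is (1 + r)/2: 0.75 at r = 0.5 and 0.85 at r = 0.7. Adjustment therefore removes 25% or 15% of the residual variance. A test with 80% power unadjusted would have about 90% or 86%.

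**Step 4: if the General covariate rule does reach 3B.** At r = 0.5 baseline CAPS-5 correlates 0.5 with both follow-up and change (√((1 − 0.5)/2) = 0.5), so it passes a 5% screen in over 99.9% of trials at n = 105. Simulating the screen followed by the chosen model (20,000 trials per setting, ρ = 0.2 and 0.3, n = 105 and 140) gives about 5% false positives at r = 0.5 and 0.7. At r = 0.3, screening on the follow-up score, it gives 6-10%.

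**Step 5: a different mechanism.** Suppose connectivity tracks true severity, CAPS-5 measures it with error, and improvement is unrelated to severity (n = 105, SD of individual improvement 0.5). The unadjusted regression then holds 5%. The adjusted one rejects in 11% at ρ = 0.3 and 26% at ρ = 0.5 with reliability 0.8, or 7% and 13% with reliability 0.9. If improvement instead rises with true severity (slope 0.3 to 0.5, reliability 0.8 to 1.0), the unadjusted model rejects in 16-59% at ρ = 0.3 and 36-96% at ρ = 0.5. The adjusted model rejects in 5-9% and 6-17%.

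**The case against.** **The General rule may already cover this.** CAPS-5 is a primary outcome, and its baseline value would almost certainly pass the screen. Step 4 shows that the excess error then largely disappears. This stands as a limit on the concern: the Step 2 rates apply only if the rule does not reach 3B. It does not settle the matter. The rule is data-dependent, does not name CAPS-5, and is absent from the 3B text, so an analyst following that text would fit the unadjusted model.

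**Adjustment is not neutral.** The null model in Step 2 is the adjusted model, so its 5% is built in. Step 5 shows a mechanism under which the change score is correct and adjustment is biased. This stands. It supports reporting both analyses, with the adjusted one as the better default.

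**Stronger readings that a reader might infer**
- *That the plan itself expects connectivity to track severity.* Power and Sample Size cites a study that "observed significant differences in PFC-AMY resting state connectivity" with d = 0.8. That study compares people with PTSD with controls. This trial enrols no controls, and a case-control difference gives no correlation with CAPS-5 among patients. It also does not address trauma-cue connectivity.
- *That everyone is selected on high symptoms.* Inclusion criterion 4 admits subthreshold PTSD, and no minimum CAPS-5 score is stated.
- *That the glutamate regressions share the gap.* Exploratory Hypothesis 4 will "examine associations between glutamate difference scores and clinical outcomes (e.g., change in total standard drinks and CAPS-5 score". The predictor there is itself a difference score, the analysis is labelled exploratory, and the calculation above does not cover it.
- *That a positive 3B result could never be interpreted.* Table 1 schedules CAPS-5 at baseline, so the dependence can be checked.

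**Conclusion.** The point holds in limited form: baseline CAPS-5 is not pre-specified in Hypothesis 3B, although it is in Hypothesis 2. Read literally, the planned regression can mistake a severity marker for a prognostic one. At r = 0.5 the false-positive rate is about 17-22% for a connectivity-severity correlation of 0.2 and 33-43% for 0.3 (n = 105 to 140; the upper end is the simulated value), against about 5% with adjustment.

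These sizes rest on three things: correlations that the documents do not give, follow-up depending on connectivity only through baseline CAPS-5, and the General covariate rule not being applied to 3B. If connectivity is unrelated to entry severity, only precision is lost. The point concerns a prognostic hypothesis under Specific Aim 3. It changes no stated sample size and leaves the Hypothesis 2 comparison untouched.

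**What to change.** In the Hypothesis 3B analysis text, state that end-of-treatment CAPS-5 (or its change) will be regressed on the connectivity estimate with baseline CAPS-5 total score as a fixed, pre-specified covariate that does not depend on the General screen. Report the unadjusted change-score regression as a sensitivity analysis. If the two disagree, the reader can see that the result depends on how entry severity is handled.

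The cost is a short addition to the plan, one degree of freedom and one extra analysis. No new data are needed.
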